6.4 Guidelines

Patient safety is paramount. The guidelines provided below are intended to provide some consistency across sites by providing guidance to be used by the Investigator, the study staff and the patient to safeguard patient safety while maintaining data integrity. The guidelines are not

intended to supersede best clinical judgment by the Investigator. Please contact the Medical Monitor with questions or with planned/known divergences from these guidelines.

1. In general, supportive care (transfusions, administration of anti-microbials, etc.) should be maintained in accordance with institutional policy. Additionally, it is advised that:
 - a. Patients with a platelet count $\leq 10 \times 10^9/L$ (10,000/ μL) be transfused.
 - b. Patients with a hemoglobin (Hb) < 8 g/dL be transfused.
 - c. Phlebotomy be performed to maintain a hematocrit $< 45\%$.
2. Patients taking medications with the potential to induce or inhibit CYP3A4 should be monitored closely for potential effects of co-administration. The Investigator may consider more frequent monitoring of complete blood count (CBC) if clinically indicated. Strong inhibitors and inducers of CYP3A4 are prohibited while on study treatment (Appendix 16.7).
3. Cessation of bomedemstat is invariably associated with a rebound in thrombopoiesis and platelet counts may easily exceed the baseline value. When bomedemstat is discontinued, the platelet count and hematocrit should be monitored closely and an alternative cyto-reductive therapy to lower platelets and hematocrit may commence within 24-48 hours, if appropriate.

6.5 Prohibited Medications/Treatments

The following medications and vaccinations are prohibited during the study. Please consult the Medical Monitor with any questions.

1. Investigational vaccines (*i.e.*, those not licensed or approved for Emergency Use) are not allowed.
Note: Any licensed COVID-19 vaccine (including for Emergency Use) in a particular country is allowed in the study as long as they are mRNA vaccines, replication-incompetent adenoviral vaccines, or inactivated vaccines. These vaccines will be treated just as any other concomitant therapy.
2. All cytotoxic agents, including hydroxyurea
3. All hematopoietic growth factors: romiplostim, eltrombopag, erythropoietin (EPO), granulocyte colony stimulating factor (G-CSF) and granulocyte-macrophage colony stimulating factor (GM-CSF)
4. Monoamine oxidase A and B inhibitors (MAOIs)
5. Anticoagulant, anti-platelet, and nonsteroidal anti-inflammatory drug (NSAID) including aspirin use is prohibited only when a patient's platelet count is $< 100 \times 10^9 /L$ (100 k/ μL)
6. Strong inhibitors and inducers of CYP3A4
7. Class 1c antiarrhythmics such as propafenone
8. Chloroquine and others whose metabolites are strong inhibitors of CYP3A4 (Appendix 16.7)

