3.6 Potential Clinical Risks and Benefits when Treating with an LSD1 Inhibitor

The treatment effects with an LSDi are distinct from treatment with standard cytotoxic agents or with JAK inhibitors. LSDi has specific effects on each myeloid lineage and appears to have different effects on each lineage for a given MPN. In wild-type healthy animals, LSD1 activity is required for the differentiation of progenitors to red cells, platelets and granulocytes. (LSD1 activity is not needed for monopoiesis.) Hence, LSDi changes the cellular composition in the marrow and the morphology of these cells. Likewise, distribution of blood cells based on lineage is also affected with an increase in the production of monocytes and a decrease in the other myeloid cell types; the production of platelets appears to be more sensitive to LSDi than granulocyte or red cell production. The treatment paradigm is to titrate drug exposure to that which lowers platelets into the normal range. The sensitivity to a given exposure of bomedemstat in PV patients, however, may be variable and understanding that dose-response is one of the objectives of this study.

The morphologic and clinical pathology changes may not be familiar to clinicians and hematopathologists. As such, there is potential for confusion in the interpretation of peripheral

hematologic parameters and the morphology of bone marrow cells. Outlined below are some of the anticipated clinical scenarios that might be observed in PV patients treated with bomedemstat based on non-clinical and clinical studies conducted by Sponsor and published reports of the effects of inhibiting LSD1:

1. With *complete* pharmacologic inhibition of LSD1, the red cell, platelet and neutrophil counts can be expected to decrease with zero order kinetics as a function of the lifespan of each cell type; hence, a linear decrease over time. Human platelets circulate for an average of seven to ten days; if LSD1 were to be inhibited completely, the platelet count would be predicted to fall below $10 \times 10^9/L$ ($10 \text{ k}/\mu\text{L}$) within a week. In this study, the goal is to safely reduce the red cell mass, as reflected by hematocrit as well as bring the platelet and WBC counts near or into the normal range. Notwithstanding, as thrombopoiesis appears most sensitive to LSDi, severe thrombocytopenia represents the greatest clinical risk.

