6.1.1 Inclusion Criteria

Patients must meet all of the applicable Inclusion Criteria and none of the Exclusion Criteria to be eligible for enrollment in this study:

1. Age ≥ 18 years.
2. History of confirmed diagnosis of Polycythemia Vera *per* World Health Organization (WHO) diagnostic criteria for myeloproliferative neoplasms (Appendix 16.2, [Arber et al., 2016](#)).
3. Bone marrow fibrosis score of Grade 0 or Grade 1, as *per* a slightly modified version (Appendix 16.3, [Arber et al., 2016](#)) of the European Consensus Criteria for Grading Myelofibrosis ([Thiele et al., 2005](#)).
4. Patients that have failed at least one standard cytoreductive therapy to lower hematocrit (failure is the equivalent of resistance or intolerance). A modified version of the European Leukemia Net (ELN) criteria for intolerance or resistance to hydroxyurea is located in Appendix 16.6, [Barosi et al., 2010](#)). Ruxolitinib and interferon refractoriness or intolerance will be left to the discretion of the Investigator.
5. Platelet count $\geq 250 \times 10^9/L$.
6. ANC $\geq 1.5 \times 10^9/L$.
7. Life expectancy > 36 weeks.
8. Able to swallow capsules.

9. Must have discontinued prior cytoreductive therapy for condition under study for 2 weeks (4 weeks for interferon) prior to study drug initiation. Phlebotomy may continue as clinically indicated.
10. Amenable to blood draws, spleen size determination, bone marrow evaluations, and peripheral blood sampling during the study.
11. Participants must agree to use an approved method of contraception from Screening until 30 days after last bomedemstat dose.

Participants Assigned Male Sex at Birth If a participant is capable of producing sperm, the participant agrees to the following during the intervention period and for at least the time needed to eliminate the study intervention after the last dose of study intervention. The length of time required to continue contraception for the study intervention is 30 days:

- Abstains from penile-vaginal intercourse as their preferred and usual lifestyle (abstinent on a long-term and persistent basis) and agrees to remain abstinent

OR

- Uses contraception as detailed below unless confirmed to be azoospermic (vasectomized or secondary to medical cause, documented from the site personnel's review of the participant's medical records, medical examination, or medical history interview) as detailed below:

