9.5.2 End of Study (EoS + 30 [±2 days])/Early Discontinuation Visit

Early Discontinuation (ED): patients should be seen in clinic as soon as possible after stopping study drug if they terminate the study early and refuse to enter the full follow-up period.

End of Study (EoS): patients should be seen in clinic 30 days (±2 days) after the last dose of study drug.

Note: The EoS visit is not required after the EoS visit for patients enrolling and starting treatment in the bomedemstat extension study.

Note: Patients may commence alternative cytoreductive therapy for their PV 24 to 48 hours after stopping treatment with bomedemstat if deemed necessary by their treating physician

The following assessments are required at the EoS/ED visit:

- AEs and Concomitant Medications
- Assess ECOG Performance Status (Appendix 16.4)
- Limited PE, including vital signs, weight, and spleen palpation
- Ensure MFSAF is completed during visit if not completed earlier in the -2 day window (see SRM for details)
- Hematology with auto or manual differential (as needed to ensure all analytes are resulted)
- Serum chemistry
- Coagulation (PT/aPTT/INR)
- Serum pregnancy test for POCBP
- Urinalysis
- Blood sample for Central Laboratory cytokine analysis
- Blood sample for Central Laboratory genomic analysis^Φ
- Blood sample for Central Laboratory correlative research^Φ
- Ensure all study medication has been returned and accounted for (if applicable)

Required at Early Discontinuation Only:

- PGIC questionnaire (see SRM for details)
- Radiologic/Imaging assessment of spleen volume (± 7 days) unless performed within the prior 5 weeks
- Bone marrow aspirate and biopsy for morphology review and correlative research^Φ (± 7 days) unless performed within the prior 5 weeks

^ΦIf possible, these bone marrow and blood samples should be collected the same day.

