12.5 Primary Analysis

Incidence of patients who achieve a sustained reduction of Hct <45% for 12 weeks without concomitant phlebotomy by Week 36 will be summarized with point estimate and its 95% CI using exact binomial method proposed by Clopper and Pearson ([Clopper and Pearson, 1934](#)). Patients not achieving a response by Week 36 or dropping from the trial but have at least one post-baseline observation will be included in the analysis as a nonresponder.

[figure not shown]
AE verbatim terms will be coded using the Medical Dictionary for Regulatory Activities (MedDRA) and summarized by treatment emergent adverse event (TEAE), Serious TEAE, related TEAE, serious related TEAE, discontinued due to TEAE, TEAE by maximum toxicity grade. Patients will be counted once per unique preferred term and body system. TEAE is defined as any event that occurs on or after the first dose of study drug administration or any preexisting event which worsened in severity after dosing. Frequency and proportion of events will be summarized.

Changes in PEs, vital signs, and laboratory values will be analyzed over time where applicable. Shift tables to worst post-baseline may be produced for specific parameters as detailed in the SAP.

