12.6 Secondary Analysis

Incidence of platelet count $\leq 450 \times 10^9/L$ will be analyzed as a proportion. Frequency and percentage of patients achieving at least one result will be counted as a reduction. Similarly, WBC $< 10 \times 10^9/L$ will be analyzed. Durability of hematocrit <45%, platelet count $\leq 450 \times 10^9/L$ and WBC $< 10 \times 10^9/L$ will be analyzed by frequency achieving at least 12, 24, 36, and 52 weeks durable responses.

New thrombotic or hemorrhagic events will be analyzed separately and combined using frequency and percentage. Each patient will be counted once per event. Reduction of spleen volume to Week 36 and Week 52 will be analyzed centrally using percent change from baseline. Change and percent change from baseline in spleen volume will be measured using a continuous measure as well. Frequency and proportion of progression will be analyzed within 36 weeks and 52 weeks. If enough events occur Kaplan-Meier estimates will be graphically displayed.

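### The prohibited-drug list, the washout and the post-treatment text differ in scope, and the scoring rules in Sections 12.5 and 12.6 can credit another cytoreductive drug's effect to bomedemstat

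*Combined protocol and SAP*

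**What the plan says.** **Before treatment.** Inclusion criterion 9 (Section 6.1.1) reads "Must have discontinued prior cytoreductive therapy for condition under study for 2 weeks (4 weeks for interferon) prior to study drug initiation". It covers cytoreductive therapy of any kind. Criterion 4 anticipates two drugs besides hydroxyurea as possible prior therapy: "Ruxolitinib and interferon refractoriness or intolerance will be left to the discretion of the Investigator".

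**During the study.** Section 6.5 and the matching synopsis list prohibit "All cytotoxic agents, including hydroxyurea". They also bar growth factors, MAO inhibitors, strong CYP3A4 inhibitors and inducers, class 1c antiarrhythmics and some other items. No item names interferon, ruxolitinib or cytoreductive therapy in general.

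**After stopping.** Section 9.5.2, with the same note in 9.5.1, says "Patients may commence alternative cytoreductive therapy for their PV 24 to 48 hours after stopping treatment with bomedemstat", if the treating physician thinks it necessary. Hematology is drawn at the End of Study (EoS) visit, 30 ± 2 days after the last dose.

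**Scoring.** The primary efficacy measure in Section 12.5 is "Incidence of patients who achieve a sustained reduction of Hct <45% for 12 weeks without concomitant phlebotomy by Week 36". Patients with no response by Week 36, or who leave the trial, count as nonresponders if they have a post-baseline observation. For platelets, and similarly for WBC, Section 12.6 says "Frequency and percentage of patients achieving at least one result will be counted as a reduction". Section 12.1 leaves detailed methods to a separate SAP.

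**The concern.** Three parts of the protocol address the same group of drugs and do not agree. The washout covers all cytoreductive therapy. The on-study list covers only the cytotoxic part of it. The follow-up text allows alternative cytoreductive therapy at a time when Section 6.5, which applies during the study, still prohibits hydroxyurea. It is doubtful that ruxolitinib can be read into the cytotoxic item, because Section 3.6 treats the two classes as separate: "The treatment effects with an LSDi are distinct from treatment with standard cytotoxic agents or with JAK inhibitors".

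The endpoint rules do not close the gap. Phlebotomy is the only co-treatment that costs a patient the primary response; an added drug does not. Section 6.7 requires stopping for treatment failure only at progressive disease, which Appendix 16.5 defines as transformation to myelofibrosis, MDS or acute leukemia. A patient whose hematocrit, symptoms or spleen are poorly controlled can therefore stay on bomedemstat.

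The trial is single-arm, so no control group offsets such credit. Compared with a rule that does not count these values, the literal rules can only give an equal or higher response count.

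**Working it through.** **1. The plan's own figure.** Section 12.2 gives 15/20 = 75% with 95% CI 50.6 to 90.4, labelled Clopper-Pearson. The exact limits are the 2.5% quantile of Beta(x, n − x + 1) and the 97.5% quantile of Beta(x + 1, n − x). With x = 15 and n = 20 they are 50.9 and 91.3. The point estimate reproduces but the interval does not; all five rows of Table 3 match the Wilson score interval with continuity correction. That is a separate matter and does not affect this point. Exact limits are used below.

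**2. Scope of the three passages.**

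| Period | Place | Scope |
|---|---|---|
| Before Day 1 | Criterion 9 | All prior cytoreductive therapy; separate period for interferon |
| During the study | 6.5, synopsis | Cytotoxic agents are the only cytoreductive class named |
| From 24–48 h after last dose | 9.5.1, 9.5.2 | Alternative cytoreductive therapy allowed |

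**3. Primary endpoint, on treatment.** The definition in 12.5 has three tests: hematocrit below 45%, for 12 weeks by Week 36, without phlebotomy. A run obtained with an added non-study cytoreductive drug passes all three. The nonresponder rule does not mention other PV drugs. All 84 days could be affected.

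**4. Primary endpoint, after the last dose.** The run needs 12 × 7 = 84 days, and scheduled hematology ends 30 days after the last dose (32 at the edge of the window).
- Days that must fall on or before the last dose: 84 − 30 = 54, or 84 − 32 = 52.
- Largest share of the run after the last dose: 30/84 = 36%, or 32/84 = 38%.

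Even this tail counts only if a patient who stops bomedemstat but attends follow-up is not treated as having left the trial. The text does not say.

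**5. Platelet and WBC incidence.** EoS falls 28 to 32 days after the last dose, and alternative therapy may start 1 to 2 days after it. If it starts in that interval, time on the new drug at the EoS sample is 28 − 2 = 26 to 32 − 1 = 31 days. One value is enough under 12.6. The result changes only for a patient with no qualifying value before the switch.

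**6. Size.** One patient in 20 is 1/20 = 5 percentage points. The documents give no count of affected responders, so 0 to 3 of an assumed 15 is shown, recoded as nonresponders:

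| Recoded | Rate | Exact 95% CI (%) |
|---|---|---|
| 0 | 15/20 = 75% | 50.9, 91.3 |
| 1 | 14/20 = 70% | 45.7, 88.1 |
| 2 | 13/20 = 65% | 40.8, 84.6 |
| 3 | 12/20 = 60% | 36.1, 80.9 |

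**The case against.** The best defence is that the intent is clear. Washout is required, and alternative therapy is described only once bomedemstat has stopped. Questions about prohibited drugs go to the Medical Monitor. The removal grounds in Section 6.3 are open-ended and include major deviations that affect study integrity. This stands as evidence of intent, but it is neither a prohibition nor a scoring rule.

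Several stronger readings do not hold:
- A reader might infer that 6.5 bars nothing but cytotoxic agents, or that it endorses combining interferon or ruxolitinib with bomedemstat. The list bars several other classes, and silence is not permission.
- A reader might infer that a primary response can be earned after treatment. It cannot be earned wholly there, since at least 52 to 54 of the 84 days precede or include the last dose.
- A reader might assume that every patient has already taken interferon or ruxolitinib. Criterion 4 requires failure of at least one standard therapy, so failure of hydroxyurea alone is enough.
- A reader might take 75% as a pass mark that one patient could flip. Section 12.2 states that all endpoints are descriptive, with no hypothesis test.

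The platelet leak is also limited. Section 6.4 expects platelets to rebound after cessation, which works against a chance qualifying EoS value, although it also means that one that does occur may reflect the next drug. Patients moving to the extension study need no EoS visit, and alternative therapy is optional.

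Finally, the SAP may contain a handling rule. It was not available, so its absence cannot be asserted.

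**Conclusion.** The point holds as a mismatch between passages plus a gap in the scoring rules. Applied literally, 12.5 credits a hematocrit run obtained under another cytoreductive drug. For the primary endpoint the exposure is the whole window on treatment, but at most about 30 to 32 of 84 days after the last dose. For platelet and WBC incidence, a single EoS value 26 to 31 days after a switch can count, and this matters only where no earlier value qualified.

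Each affected patient moves a rate by 5 points, assuming 20 analyzed patients. How many would be affected is unknown; the range of 0 to 3 above is an assumption. The conclusion rests on the protocol text and would be narrowed by any scoring rule in the SAP.

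**What to change.** 1. Reconcile the drug list in Section 6.5 and the synopsis with criterion 9 and with Sections 9.5.1 and 9.5.2, in both scope and timing. Which drugs are permitted, and when, is for the sponsor to decide.
2. In 12.5, state that a 12-week run containing any non-study cytoreductive drug does not count as a response. Say also whether stopping bomedemstat before Week 36 counts as leaving the trial. Use the same definition for the interim summary in 12.8.
3. In 12.6, count only values up to the last bomedemstat dose and before any non-study cytoreductive drug.
4. Carry these rules into the SAP.

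The cost is a few sentences. Concomitant medications are already collected at the scheduled clinic visits, so no new data are needed. The downside is that reported rates may be slightly lower.

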6.6 Patients Who Terminate Early or Discontinue Study Medication

All patients who terminate the study early or discontinue bomedemstat, including those who discontinue bomedemstat due to an event meeting any of the Stopping Rules as *per* Section 8.2.3, will be requested to return for follow-up visits, beginning with an EoT visit as detailed in

Section 9.5.1. If a patient refuses to enter follow-up, then an Early Discontinuation (ED) visit should be performed as detailed in Section 9.5.2.

6.7 Treatment Failure

Patients not deriving clinical benefit (*i.e.*, those meeting “progressive disease” criteria as *per* Appendix 16.5) will discontinue bomedemstat and undergo EoT and EoS visits.

7 STUDY TREATMENT

7.1 Formulation, Labeling, Packaging and Storage

7.1.1 Formulation

The drug product is bomedemstat, a bis-tosylate salt. The free base of bomedemstat is the active moiety. Bomedemstat will be supplied in capsules of multiple strengths. These strengths, based on bomedemstat free base, *i.e.*, the active substance, may include: 5 mg, 10 mg, 25 mg, and 50 mg. Additional strengths may be added over the duration of the study. Details on capsules, including strengths, colors and sizes, can be found in the Pharmacy Manual.

The capsules will be manufactured in accordance with Annex 13 and principles of current Good Manufacturing Practices (cGMP) at:

Xcelience LLC
[name]
[name]

Changes to this section will be included *via* updates to the Pharmacy Manual and/or notifications to sites, as appropriate.

7.1.2 Packaging and Labeling

Bomedemstat will be supplied to the site by Sponsor (or designee) in bottles containing capsules in accordance with all applicable regulatory requirements. Labels will also be in accordance with all applicable regulatory requirements for the labeling of active pharmaceutical ingredients and with Annex 13 of GMP. Labels will contain the drug name, protocol number, lot number, expiry date, storage conditions, name of the (local) Sponsor and a caution that drug is for clinical trials use only.

7.1.3 Storage

The recommended long-term storage conditions for bomedemstat are for the storage temperature not to exceed 25°C. Bomedemstat supplies must be stored in a secure area with access limited to the Investigator and authorized staff, under physical conditions consistent with bomedemstat-specific requirements and under the appropriate conditions according to the country, state and regional laws. Procedures for bomedemstat storage and accountability will be detailed in a Pharmacy Manual.

7.2 Dispensing, Administration, Dosage and Missed Doses

7.2.1 Dispensing

All material supplied is for use only in this clinical study and should not be used for any other purpose. Only patients enrolled in the study may receive study drug, in accordance with all applicable regulatory requirements. Only authorized site staff may dispense study drug.

The Investigator is responsible for bomedemstat accountability, reconciliation and record maintenance (Section 14.5). The Investigator must provide a prescription form every time drug is dispensed, including (but not limited to) the: identification of the patient to whom drug is to be dispensed, patient's weight, requested dose in mg/d and Investigator (or designee's) signature.

Bomedemstat will be dispensed in accordance with the dose chart provided.

